5. DEFINITIONS

The terms study site and center are used interchangeably.

Time 0 is defined as the start time of study drug administration for the PK analyses, and as the end time of surgery for the efficacy analyses.

Study day: Day 1 is defined as the day study drug is administered. Positive study days will be measured forward in time from Day 1, with Day 2 being the calendar day immediately following the day study drug is administered. Day -1 is the calendar day immediately preceding the day study drug is administered and negative study days will be measured backward from Day -1.

Study visits and time points will be determined from the scheduled times as reported on the electronic CRFs (eCRFs) for the summarization and analysis of data that are shown by time point, unless otherwise specified.

6. ANALYSIS SETS

The safety analysis set will include all subjects who receive study drug and will be based on actual treatment received.

The efficacy analysis set will include all subjects in the safety analysis set who undergo the planned surgery and will be based on randomized treatment, regardless of actual treatment received.

The PK analysis set will include all subjects in the safety analysis set who receive liposome bupivacaine, provide sufficient samples to allow for calculation of PK parameters required for analysis, and who do not receive conventional bupivacaine HCl postsurgically.

7. STATISTICAL METHODS OF ANALYSIS

7.1. General Principles

Descriptive statistics (the number of subjects [n], mean, standard deviation [SD], median, minimum, and maximum) will be used to summarize continuous variables. Means and medians will be presented to one more decimal place than the recorded data. Standard deviations will be presented to two more decimal places than the recorded data. Minimum and maximum values will be presented using the same number of decimal places as the recorded data. Percentages will be presented to one decimal place.

In addition, for PK parameters, geometric means and between-subject coefficient of variations (%CV) will be presented.

Frequency distributions (number [n] and percentage of subjects [%]) will be used to summarize categorical or qualitative variables. In general, the denominator for the percentage calculation will be based upon the total number of subjects in the study population for the treatment groups, unless otherwise specified.

All statistical tests will be performed against a two-sided alternative hypothesis with a significance level of 5% ($\alpha = 0.05$), and all confidence intervals (CIs) calculated will be two-sided 95% CIs. All tests will be declared to be statistically significant if the calculated p-value is ≤ 0.05 unless specified otherwise. Tests for binomial proportions will be conducted (1) using a normal approximation whenever each classification cell for each group to be compared contains expected cell counts of 5 or more subjects, or (2) using an exact method whenever any one classification cell for any one group to be compared contains expected cell counts of fewer than 5 subjects.

All analyses will be performed using SAS[®] Software version 9.2 or later.

Pharmacokinetic parameters will be derived using noncompartmental methods with WinNonlin[®] Professional Version 5.2 or later (Pharsight Corp., Cary, North Carolina).

For the listings, subjects will be listed under their randomized treatment, regardless of actual treatment received. Subjects who are randomized but do not receive study drug will be included in the listings with the treatment group identified as “Liposome bupivacaine xx mg, Not Treated” or “Placebo, Not Treated”, depending on their randomized treatment.

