15.7. Significance Testing

All tests will be two-sided and based on a significance level of 0.05.

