3. STUDY OBJECTIVES

Part 1: The primary objectives of Part 1 are to (1) evaluate three dose levels of liposome bupivacaine versus placebo with respect to the magnitude and duration of the analgesic effect achieved following single dose injection femoral nerve block with liposome bupivacaine, and (2) select a single therapeutic dose of liposome bupivacaine from the three dose levels to be tested in Part 2.

Part 2: The primary objective of Part 2 is to compare the magnitude and duration of the analgesic effect of single injection femoral nerve block of a single dose level of liposome bupivacaine (selected from Part 1) with placebo (preservative-free normal saline for injection).

The secondary objectives are to evaluate additional efficacy parameters, characterize the pharmacokinetic (PK) profile of liposome bupivacaine when administered as a femoral nerve block, and further assess the safety profile of liposome bupivacaine.

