7.1.4. Multiplicity Adjustments

Part 1

The purpose of Part 1 of the study is to select a dose for use in Part 2. Therefore, no alpha-level adjustments for multiple comparisons between the three doses and placebo will be made.

Part 2

Since no multiple comparisons of the primary efficacy variable will be made, no alpha-adjustments will be made.

Also, since there is only one primary efficacy variable and all other efficacy variables are considered secondary, no alpha-adjustments for the primary response variable will be made.

There are two secondary efficacy variables that will be analyzed using a hierarchical fixed-sequence stepwise testing procedure (See [Section 7.6.1](#)). The two secondary efficacy variables will only be analyzed if the primary efficacy variable is statistically significant at the two-sided 0.05 significance level. To protect the Type 1 error rate, the testing will be performed in a sequentially rejective fashion. First, the total postsurgical opioid consumption through 72 hours will be tested. If the test of opioid consumption is significant at the two-sided 0.05 level then, and only then, the time to first opioid rescue will be tested. Each test will be declared positive at the two-sided 0.05 significance level.

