7.6.2.3 Tertiary Efficacy Variables

For Part 1, no statistical tests will be performed on any of the tertiary efficacy variables. Only descriptive statistics will be shown for each treatment.

For Part 2, the following describes the statistical analyses to be performed.

NRS-R, NRS-A, and AUC of Pain Intensity Scores

For the tertiary efficacy variables NRS-R, NRS-A, and the AUCs of the NRS-R and NRS-A pain intensity scores, the same analyses as those for the primary efficacy variable will be performed, except that the baseline NRS-A score will be used as the covariate for all variables using the NRS-A.

Proportion of Subjects Who are Pain Free

Pain free is defined as an NRS-R pain intensity score of 0 or 1. The number and percentage of subjects who are pain free will be summarized by treatment group for each time point. A chi-square test will be used to compare liposome bupivacaine to placebo.

Total Postsurgical Opioid Consumption Through 24, 36, 48, and 60 Hours

For the tertiary efficacy variables total opioid consumption through each of the time periods, the same analysis as that for the secondary efficacy variable of total opioid consumption through 72 hours will be performed.

Subjects Who Receive Rescue Medication

The category of ‘Subjects who receive no rescue medication’ is defined as subjects who report not taking any medication on the four Rescue Medication eCRFs.

The category of ‘Subjects who only receive the IV hydromorphone bolus’ is defined as subjects who report taking IV hydromorphone (or other opioid medications) on the First Rescue Medication eCRF and report not taking a medication on either of the Second Rescue Medication eCRFs or on the Third Rescue Medication eCRF.

The category of ‘Subjects who receive the IV hydromorphone bolus and a second opioid medication’ is defined as subjects who report taking IV hydromorphone (or other opioid medication) on the First Rescue Medication eCRF and who report taking a medication on either of the Second Rescue Medication eCRFs and report not taking a medication on the Third Rescue Medication eCRF.

The category of ‘Subjects who receive the IV hydromorphone bolus, a second opioid medication, and conventional bupivacaine HCl’ is defined as subjects who report taking IV hydromorphone (or other opioid medication) on the First Rescue Medication eCRF, who report taking a medication on either or both of the Second Rescue Medication eCRFs, and bupivacaine HCl on the Third Rescue Medication eCRF.

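### SAP 7.1 allows any of 52 ungated Part 2 tertiary tests, including the only ones that isolate late effect, to be declared statistically significant at p ≤ 0.05 even if the primary fails

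*SAP*

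**What the plan says.** **General rule.** SAP 7.1 sets a two-sided 5% level and then says: "All tests will be declared to be statistically significant if the calculated p-value is" at or below "0.05 unless specified otherwise". Protocol 15.7 is equally general: "All tests will be two-sided and based on a significance level of 0.05".

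**Exception.** SAP 7.1.4 says: "There are two secondary efficacy variables that will be analyzed using a hierarchical fixed-sequence stepwise testing procedure". It adds a gate: "The two secondary efficacy variables will only be analyzed if the primary efficacy variable is statistically significant at the two-sided 0.05 significance level". SAP 7.6.2.2 repeats the order, opioid consumption through 72 h and then time to first opioid rescue. Nothing else in the SAP departs from the general rule for Part 2.

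**Tertiary variables.** SAP 7.6.2.3 names a test for every Part 2 tertiary variable. For the NRS scores and AUCs, "the same analyses as those for the primary efficacy variable will be performed", which includes a p-value. The Part 2 shells carry p-values for these variables, among them Table 14.2.2.8-2 for AUC 24-48 h and 48-72 h. No section gates these tests on the primary, adjusts them, or calls them nominal or descriptive.

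**Contrast within the SAP.** For Part 1, 7.6.2.3 limits the tertiary variables to descriptive statistics. Section 2 uses the word exploratory only for post-hoc or unplanned work, and allows the planned analyses into study reports, submissions and manuscripts.

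**Objective.** SAP Section 3 gives the Part 2 primary objective as to "compare the magnitude and duration of the analgesic effect of single injection femoral nerve block" at the selected dose with placebo.

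**The concern.** The general rule is an instruction to declare significance, and the exception does not reach the tertiary tests. Suppose the primary AUC through 72 h gives p = 0.06. Under SAP 7.1.4, opioid consumption through 72 h may then not be analysed. Opioid consumption through 60 h is tertiary and uses the same ANOVA on log totals, and SAP 7.1 would have it declared significant at p ≤ 0.05. AUC of NRS-R through 60 h is in the same position. A near copy of a closed test stays open.

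The late-effect analyses sit in the same set. AUC through 72 h and opioid use through 72 h both span the late period but average over it. Time to first rescue concerns the start of need. Only AUC 24-48 h, AUC 48-72 h and the NRS scores by time point separate late effect from early effect, and none of them is controlled. At stake is how the report words its findings on duration, and whether a failed primary could be followed by results described as statistically significant.

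**Working it through.** **The plan's own figure.** The documents state no error rate for the tertiary tests. The one related figure is the primary's power in SAP Section 8: difference 61, SD 104, 90 per group, two-sided 0.05, power above 97%. This reproduces at 97.6% (normal approximation) and 97.5% (noncentral t). It concerns the primary only and is not affected by this point.

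**Count of Part 2 tertiary tests** (variables from SAP 7.6.1, tests from 7.6.2.3, NRS time points from protocol 13.5):

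| Variable | Tests |
|---|---|
| NRS-R at 2, 4, 8, 12, 24, 36, 48, 60, 72 h | 9 |
| NRS-A at the same times | 9 |
| AUC NRS-R through 24, 36, 48, 60 h | 4 |
| AUC NRS-A through 24, 36, 48, 60, 72 h | 5 |
| AUC NRS-R 24-48 h, 48-72 h | 2 |
| Pain free at 9 times | 9 |
| Opioid consumption through 24, 36, 48, 60 h | 4 |
| Rescue categories | 4 |
| OBAS at 24, 48, 72 h | 3 |
| Subject satisfaction at 72 h, Day 30 | 2 |
| Time to sensitivity to cold | 1 |
| **Total** | **52** |

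Shell Tables 14.2.2.4-2 and 14.2.2.5-2 also show p-values at first request, which makes 54. Not counted: five Part 2 safety tests (walk test at three times, physician satisfaction at two; SAP 7.8.4) and the ORAE test, which is Part 1 only.

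**Expected false positives if the block has no effect on anything:**
- 52 × 0.05 = 2.6, whatever the correlation between tests.
- The tests are two-sided, so those favouring the drug number 52 × 0.025 = 1.3.

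**Chance of at least one p ≤ 0.05:**
- Independent tests: 1 − 0.95^52 = 0.931. In the drug's favour: 1 − 0.975^52 = 0.73.
- Independence cannot hold here. The cumulative AUCs are nested, they are built from NRS scores that are also tested singly, pain-free status is a cut of NRS-R, and the opioid totals accumulate. The documents give no correlations, so a common correlation is assumed and varied (equicorrelated normal statistics, 200,000 simulated draws, either direction):

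| Assumed correlation | At least one of 52 | At least one of the two late-interval AUCs |
|---|---|---|
| 0 | 93% | 9.75% |
| 0.3 | 81% | 9.5% |
| 0.5 | 63% | 9.1% |
| 0.7 | 41% | 8.2% |
| 0.9 | 19% | 7.0% |

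Every entry exceeds 5%. Correlation makes false positives rarer but clusters them: at 0.7, 59% of null trials show none, and those with any average about 2.6 / 0.41 = 6.3.

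**After the change.** With declarations limited to the primary and the two gated secondaries, the familywise error for declared results is at most 0.05. Appending the two late-interval AUCs in order keeps it there, because each test is reached only if every earlier one is significant.

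**The case against.** The strongest reply is that these variables are ranked third in both documents, that protocol 15.1 states a single Part 2 null hypothesis, and that applying an ordinary 0.05 level to supportive endpoints is common practice. LS mean differences or ratios with 95% CIs are already planned for the NRS, AUC and opioid variables. On this view only a label is missing.

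Much of this stands:
- A reader might infer that the general rule defeats the hierarchy. It does not. The tertiary tests spend none of the sequence's alpha, and the three confirmatory tests stay controlled at 0.05.
- A reader might infer that the sponsor plans claims from tertiary results. No section says so.
- A reader might infer that duration has no controlled evidence. The primary and the first secondary both run to 72 h and so cover the late period, though neither isolates it. The objective does not promise interval-specific inference.
- The 93% figure needs an independence these endpoints lack, and only half of the expected false positives would favour the drug.

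Rank alone does not close the gap. SAP 7.1 is an active rule with a stated way to make exceptions, and the tertiary tests have no exception. The SAP restricts tertiary inference in Part 1 but not in Part 2. SAP 7.1.4 also blurs the tiers by describing all efficacy variables other than the primary as secondary before naming only two.

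**Conclusion.** The point holds as a gap in what may be declared significant outside the controlled family. The primary and secondary conclusions are unaffected. As written, any of 52 Part 2 tertiary tests (54 with first request) may be declared statistically significant at p ≤ 0.05, even after the primary has failed.

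The expected number under a global null is 2.6, of which 1.3 favour the drug; this follows from the count and the level alone. The chance of at least one ranges from about 19% to 81% for assumed common correlations of 0.9 down to 0.3, with 93% as the independent extreme. A single common correlation is a simplification, so these figures are illustrative.

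**What to change.** **Main change, SAP 7.1.** State that in Part 2 statistical significance is declared only for the primary variable and, in the order and under the gate of 7.1.4, the two secondary variables. All tertiary and safety p-values are reported as nominal, beside the estimates and 95% CIs already planned where these exist. The sentence in 7.1.4 that treats every non-primary variable as secondary should be brought into line with the three tiers.

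This needs wording only: no new data and no change to sample size or to the primary's power. The downside is that fewer results can be called significant.

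**Optional.** If a late-effect claim is wanted, append AUC NRS-R 24-48 h and then 48-72 h to the end of the fixed sequence, each at two-sided 0.05, before Part 2 is unblinded. The earlier tests lose no alpha, but the late tests are reached only if the primary and both secondaries succeed. This goes beyond the SAP. Protocol 12.2 ranks these AUCs as tertiary, and 12.2 and 15.6.3.2 fix the sequence at two named secondaries, so both sections need a matching change.

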7.1.1. Calculation of AUC of NRS

Area under the curve (AUC) will be calculated using the trapezoidal method with the actual NRS pain intensity scores reported by the subject. Missing values will be imputed as described in [Section 7.1.3](#). The time points “Baseline” and “First Rescue” will not be included in the calculation of AUC. However, “First Rescue” might be used for imputation purposes as described in [Section 7.1.2](#). Time 0 NRS score will be set to a score of 0. Actual times, not scheduled times, when available will be used in the calculations. Linear interpolation will be used to calculate the pain intensity score at the end of an interval. For 72 hours, as an example, if the actual time is prior to 72 hours post-dose then the actual time

and the reported score will be used. In addition, the reported score will be carried forward to 72 hours. If the actual time is after 72 hours then linear interpolation between the 60-hour and 72-hour scores will be used to calculate the score at 72 hours and the time will be set to 72. The linear interpolation will be performed after missing pain scores are imputed as discussed in Section 7.1.2.

7.1.2. Imputation of NRS Pain Intensity Scores

For calculation of AUC of NRS pain intensity scores, the windowed worst observation carried forward (wWOCF) and last observation carried forward (LOCF) imputation procedure will be used as follows:

- a) Windowed worst observation carried forward for rescue medications

For subjects who take a rescue medication, their NRS scores recorded within the window of controlled type of rescue medication (see the table below for the windows for the planned rescue medications) will be replaced by the ‘worst’ observation. The worst observation will be the highest score in the time interval from Time 0 to up to the time prior to taking the first rescue medication. The NRS score at the first rescue will be included in this calculation. Note that NRS scores in the window that are higher than the worst value prior to rescue medication will not be overwritten. If no NRS score is available prior to the first rescue the worst observation from all available NRS scores will be used instead.

Medication	Route	Window Used to Impute NRS
Oxycodone	PO	6 hours
Oxycontin (MS Contin)	PO	6 hours
Morphine	IV	4 hours
Hydromorphone (Dilaudid)	IV	2 hours
Hydromorphone (Dilaudid)	PO	4 hours
Fentanyl	IV	6 hours
Fentanyl	Transdermal	Start of administration until the end of the administration plus 6 hours
Hydrocodone	PO	6 hours
Bupivacaine HCl	Perineural	12 hours
Bupivacaine HCl	Infusion	Start of the infusion until the end of the infusion plus 12 hours

Ropivacaine		Start of the infusion until the end of the infusion plus 12 hours
Meperidine	IV	4 hours
Ultram	PO	6 hours

IV = intravenous; PO = oral.

If unplanned rescue medications are given then the window will be determined post-hoc prior to breaking the blind. If a combination opioid is given then the window will be determined by the opioid part of the medication. Opioids given postsurgically with an indication like ‘anesthesia maintenance’ will not be included for imputation purposes.

- b) Missing scores before the first non-missing score will be replaced by the median score at the missing time point from the other subjects in the same treatment group.
- c) Missing scores after the last non-missing score will be replaced by the LOCF.
- d) Missing scores between two non-missing scores will not be replaced (i.e., linear interpolation will be used).

Subjects who have no pain intensity scores recorded after surgery will have the missing scores replaced by the median score at each time point from all subjects in the same treatment group.

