15.6.3.1 Primary Efficacy Measure

The primary efficacy measure in this study is the AUC of the NRS-R pain intensity scores through 72 hours.

Handling of Subjects Requiring Rescue Medication

For AUC of the NRS-R and NRS-A pain intensity scores, prior to analysis the windowed Worst-Observation-Carried-Forward (wWOFCF) imputation method will be applied. For subjects who take rescue pain medication, their pain intensity scores recorded within the window of controlled type of rescue medication (6 hours for oxycodone, 4 hours for morphine, and 2 hours for IV hydromorphone) will be replaced by the ‘worst’ observation. For subjects who require a rescue with conventional bupivacaine HCl, the window will be from the start of the bupivacaine infusion until the end of the infusion plus 12 hours. All pain scores within that window will be replaced by the ‘worst’ observation. The worst observation will be the highest score in the time interval from the end of surgery up to the time prior to taking their first rescue pain medication. Note that pain intensity scores in the window that are higher than the worst value prior to rescue pain medication will not be overwritten. If no pain intensity score is available prior to the first rescue pain medication, the worst observation from all available measurements will be used instead.

Part 1

For AUC of the NRS-R pain intensity scores through 72 hours, each dose of liposome bupivacaine will be compared to placebo using analysis of covariance (ANCOVA) with treatment as the main effect and the baseline NRS-R pain intensity score as the covariate. Based on the model, the difference between each dose of liposome bupivacaine and placebo will be estimated along with the 2-sided 95% confidence interval (CI).

Part 2

For AUC of the NRS-R pain intensity scores through 72 hours, liposome bupivacaine will be compared to placebo using ANCOVA with treatment as the main effect and the baseline NRS-R pain intensity score as the covariate. Based on the model, the difference between the treatment groups will be estimated along with the 2-sided 95% CI.

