7.6.1. Efficacy Variables

The primary efficacy variable is the AUC of the NRS-R pain intensity scores through 72 hours.

Secondary efficacy variables are:

- Total postsurgical opioid consumption (in mg) through 72 hours.
- Time to first opioid rescue.

Tertiary efficacy variables are (the order of these variables has been changed from the order in the protocol to reflect how they will be discussed in the CSR):

- The NRS-R and NRS-A pain intensity scores at each assessed time point.
- The AUC of the NRS-R pain intensity scores through 24, 36, 48, and 60 hours.

- The AUC of the NRS-A pain intensity scores through 24, 36, 48, 60, and 72 hours.
- The AUC of the NRS-R pain intensity scores from 24-48 and 48-72 hours.
- Proportion of subjects who are pain free (defined as an NRS pain intensity score of 0 or 1) at each assessed time point.
- Total postsurgical opioid consumption (in mg) through 24, 36, 48, and 60 hours.
- Proportion of subjects who receive the following rescue medication(s):
 - Subjects who receive no rescue medications (i.e., opioid or conventional bupivacaine HCl).
 - Subjects who only receive IV hydromorphone bolus.
 - Subjects who receive IV hydromorphone bolus and a second opioid medication.
 - Subjects who receive IV hydromorphone bolus, a second opioid medication, and conventional bupivacaine HCl.
- Overall benefit of analgesia score questionnaire at 24, 48, and 72 hours.
- Subject satisfaction with postsurgical pain control at 72 hours and Day 30.
- Time to sensitivity to cold (listed in the protocol as proportion of subjects at each time point with sensitivity to cold on one of the dermatomes).
- Incidence of predefined treatment-emergent ORAEs (diffuse pruritus, overt respiratory depression, urinary retention as measured by need for postsurgical bladder catheterization, constipation, sedation, confusion, delirium, vomiting, or need for antiemetic medication) at 72 hours (Part 1 only).

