8. SAMPLE SIZE CALCULATIONS

Part 1

The sample size for Part 1 of the study was not based on formal statistical power calculations.

Part 2

A study population of approximately 180 subjects is planned with approximately 90 subjects in each treatment group (liposome bupivacaine and placebo). The sample size was estimated based on the results of a Phase 3 hemorrhoidectomy study of liposome bupivacaine versus placebo where the mean (SD) AUC of the NRS-R pain intensity scores through 72 hours was 141 (101) and 202 (104) for the liposome bupivacaine and placebo groups, respectively.

A two-group t-test with 0.05 two-sided significance level will have >97% power to detect a difference in means of 61, assuming that the common SD is 104, when the sample size in each group is 90.

After the data from Part 1 are evaluated, the sample size for Part 2 may be increased. The evaluation of the data did not indicate that the sample size should be increased.

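### The 24-48 h and 48-72 h NRS-R AUCs are planned only with low rescue-window scores raised to the worst score before the first rescue, so early pain can create or shrink a late difference

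*SAP*

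**What the plan says.** SAP 3 sets the aim: "The primary objective of Part 2 is to compare the magnitude and duration of the analgesic effect". SAP 7.6.1 lists among the tertiary variables "The AUC of the NRS-R pain intensity scores from 24-48 and 48-72 hours"; every other NRS AUC in that list starts at Time 0.

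SAP 7.1.2 applies one imputation to all of them: "For calculation of AUC of NRS pain intensity scores, the windowed worst observation carried forward (wWOCF) and last observation carried forward (LOCF) imputation procedure". Item (a) gives the replacement value, with first rescue as the cut-off: "The worst observation will be the highest score in the time interval from Time 0 to up to the time prior to taking". By item (a), a score recorded at first rescue counts as well. Protocol 15.6.3.1 uses the same anchor and the same cut-off: "The worst observation will be the highest score in the time interval from the end of surgery up to the time prior".

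Item (a) has two limits. Only scores inside a rescue window are replaced (6 h for oral oxycodone, 4 h for IV morphine, 2 h for IV hydromorphone, longer for perineural local anaesthetic). A score in a window that is already above the anchor is kept.

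Tables 14.2.2.8-1 and 14.2.2.8-2 present the two interval AUCs with wWOCF + LOCF only. In Part 2 they receive the primary-type ANCOVA with a confidence interval and p-value (SAP 7.6.2.3). The single sensitivity analysis in SAP 7.6.2.1 concerns the primary variable and keeps wWOCF.

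**The concern.** The anchor is set once and never updated. A 60 h score taken within 6 h of an oxycodone dose is compared with pain before the first rescue, not with pain before that dose. If that earlier pain was worse, it becomes the 60 h value.

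A reader will naturally turn to the 24-48 h and 48-72 h AUCs to judge how long the effect lasts. If the arms differ in pain before first rescue, the rule can carry that difference into both late intervals even when late pain is the same. If the arms have similar pain before first rescue, a real late difference can be flattened. The interval estimate and p-value in the report would then partly describe early pain.

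**Working it through.** **The plan's own figure.** The only stated power concerns the primary AUC through 72 h (SAP 8): "A two-group t-test with 0.05 two-sided significance level will have >97% power to detect a difference in means of 61". The same section supplies an SD of 104 and 90 subjects per arm. Standard error = 104 × √(2/90) = 15.50; 61/15.50 = 3.93; power = Φ(3.93 − 1.96) = 97.6% (97.5% with the noncentral t, 178 df). It reproduces. The documents give no figure for the interval AUCs, so the 61 NRS-hours serves only as a yardstick.

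**Rule and formula.** Scores fall at 24, 36, 48, 60 and 72 h (Protocol 12.1). At nominal times AUC48-72 = 6·s48 + 12·s60 + 6·s72, and likewise for 24-48 h. A score in a window becomes max(recorded, anchor); any other score is unchanged.

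**Worked pairs, all three scores in windows.**
- Late scores 3 and 3, anchors 8 and 5: recorded 24 × 3 = 72 for both; imputed 24 × 8 = 192 and 24 × 5 = 120. A difference of 0 becomes 72.
- Late scores 5 and 2, anchors 7 and 7: recorded 120 and 48; imputed 168 and 168. A difference of 72 becomes 0.
- Late scores 9 and 5, anchors 6 and 6: recorded 216 and 120; imputed 216 and 144. A difference of 96 becomes 72, so most of it survives.
- No late score in a window: imputed equals recorded.

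**Window coverage.** With evenly spaced doses, coverage = min(1, window/spacing). Oxycodone (6 h window; the plan permits spacing down to 4 h): every 4 to 6 h 100%, every 8 h 75%, every 12 h 50%.

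**Group level.** If all windowed scores lie below the anchor, the carried-over difference per 24 h interval = 24 × mean anchor difference × share of scores in windows. For an assumed 1-point anchor difference and 50-100% coverage this is 12 to 24 NRS-hours per interval, or 24 to 48 over 24-72 h.

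**Simulation, 24-48 h AUC, on assumed inputs.** 90 per arm, 4,000 replicates, two-sided 0.05 t-test without the baseline covariate. Assumed: mean anchor 7 (SD 1.8), mean late score 4 (SD 2.0), within-subject correlation 0.4, and equal window coverage in both arms. Each cell gives the mean difference (drug minus placebo) and the proportion of trials significant in favour of drug.

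| Share of late scores in windows | No late effect, anchor 1.5 lower on drug | Late effect 1.5 points, equal anchors |
|---|---|---|
| Recorded scores | about 0; 2.3-2.7% | about −34; about 100% |
| 25%, wWOCF | −7.4; 23% | −25.8; 98% |
| 50%, wWOCF | −14.9; 67% | −17.7; 73% |
| 75%, wWOCF | −22.4; 96% | −9.5; 29% |
| 100%, wWOCF | −29.9; 99.9% | −1.3; 4% |

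The limit works the other way when late pain is high. With mean late score 7, anchors of 5 and full coverage, the late difference goes only from −34.8 to −24.8, and 99.6% of trials remain significant.

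**The case against.** **Recorded scores are not the truth either.** A score taken within hours of an opioid dose is partly suppressed, and wWOCF was pre-specified in the protocol to deal with that. This stands. It is a reason not to replace one version by the other. It is not a reason to show a day 2 or day 3 result only with a value fixed before the first rescue.

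**Other planned analyses bear on duration without wWOCF.** These are time to first opioid rescue, NRS-R and NRS-A at each time point with ANCOVA, the pain-free proportion, and cumulative opioid use. SAP 7.1.2 confines the imputation to AUCs, and Tables 14.2.2.4-2 and 14.2.2.5-2 carry no wWOCF label, so late scores appear to be reported there as recorded. At nominal times and apart from missing data, the recorded-score AUC24-48 difference is 6, 12 and 6 times the time-point differences. This stands as a partial offset; the confidence interval for the interval AUC is what cannot be recovered.

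**Stronger readings that the text does not support.**
- A reader might infer that the late intervals are simply filled with early pain, whatever late pain was. Both limits in item (a) rule that out.
- A reader might assume that first rescue usually comes within hours of surgery. Its timing is an endpoint and no value is given; if the block delays rescue, the anchor period may reach day 2.
- A reader might take the interval AUCs as the stated measure of duration, so that this part of the objective is answered only from early pain. No sentence gives them that role, and the analyses above do not use the anchor.

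**Conclusion.** The concern holds, with limits. As planned, the two interval AUCs can report a late difference that reflects pain before first rescue, or understate one that exists, under rescue patterns the plan permits. Two conditions are needed together: a substantial share of late scores in rescue windows, and late pain below the anchor. Where either is missing, the imputed AUC stays close to, or equals, the recorded one.

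The worked pairs follow from the rule alone. The 12 to 24 NRS-hours and the simulation rest on assumed anchors, late scores and coverage, and are not forecasts for this trial.

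The consequence is for interpretation. These variables are tertiary and outside the testing hierarchy in SAP 7.1.4, Part 1 runs no tests on them, and Table 14.2.2.8-1 is not among the dose-selection tables in SAP 7.9. It would go too far to infer that the primary test, its error rate or the dose selection is affected by this point. What is affected is how much a claim of effect in 24-48 h or 48-72 h can rest on these AUCs.

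**What to change.** In SAP 7.6.2.3 and Tables 14.2.2.8-1 and 14.2.2.8-2:

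- Add both interval AUCs computed from recorded scores (omit step (a) of SAP 7.1.2, keep (b) to (d)), with the same ANCOVA in Part 2.
- Report per arm the share of 24-72 h scores replaced under wWOCF.
- Label the wWOCF rows as anchored to pain before first rescue.
- State that a claim of effect in either interval will not rest on the wWOCF rows alone, but will be read with the recorded-score rows and with morphine-equivalent use in the same interval.
- For interval opioid use, flag or exclude subjects whose PCA interval record spans 24 or 48 h, and identify projected amounts. SAP 7.1.3 books the whole dose of such a record at its start and projects use for early discontinuers, so simple subtraction of cumulative totals can put opioid in the wrong interval.

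Leave the primary AUC through 72 h unchanged.

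The cost is SAP wording and extra table rows. No new data are needed: Listing 16.5.1.1 already holds actual and imputed scores. The drawbacks are that recorded scores are partly opioid-suppressed, that LOCF can carry a suppressed last score forward in subjects withdrawn for inadequate relief, and that the duration result may look less favourable.
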